### **7.6. Other Safety Measures**

All post treatment anti-cancer therapies (other than those allowed per-protocol) will be provided in a by-subject listing sorted by subject ID number and administration date in chronological order. A summary of post treatment anti-cancer therapies will not be provided.

A data listing will be provided for the results of all pregnancy tests conducted in the study.

### **7.7. Changes from Protocol-Specified Safety Analyses**

Continuous safety data including laboratory data will not be summarized.

## 8. PHARMACOKINETIC (PK) ANALYSES

### 8.1. PK Sample Collection

Plasma samples will be collected to measure concentrations of ADX at protocol specified time points.

#### 8.1.1. Estimation of PK Parameters

For subjects in Cohort 1, relevant PK parameters will be estimated using Phoenix WinNonlin® software and utilizing standard noncompartmental methods. The linear/log trapezoidal rule will be used in conjunction with the appropriate noncompartmental model, with input values for dose level, dosing time, plasma concentration, and corresponding real time values, based on drug dosing times whenever possible. Descriptive statistics will be presented for PK parameters of ADX by cohort.

All predose sample times before time-zero will be converted to 0. For area under the curve (AUC), samples BLQ of the bioanalytical assays occurring prior to the achievement of the first quantifiable concentration will be assigned a concentration value of 0 to prevent overestimation of the initial AUC. Samples that are BLQ at all other time points will be treated as missing data in WinNonlin. The nominal time point for a key event or dosing interval ( $\tau$ ) may be used to permit direct calculation of AUC over specific time intervals. The appropriateness of this approach will be assessed by the PK scientist on a profile by profile basis.

Pharmacokinetic parameters such as  $\lambda_z$  and  $t_{1/2}$  are dependent on an accurate estimation of the terminal elimination phase of drug. The appropriateness of calculating these parameters will be evaluated upon inspection of PK data on a profile-by-profile basis by the PK scientist.

#### 8.1.2. PK Parameters

The PK parameters for ADX presented in the table below will be computed for all subjects in the PK Analysis Set, as applicable.

The analytes and parameters presented in [Table 8-1](#) will be used to evaluate the PK objectives of the study. The primary PK parameters are  $AUC_{last}$  and  $C_{max}$  of ADX. The PK parameters to be estimated in this study are listed and defined in the PK Abbreviations section.

**Table 8-1. PK Parameters for Each Analyte**

Analyte	PK Parameters
ADX	$C_{eoi}$ , $C_{max}$ , $T_{max}$ , $AUC_{last}$ , $AUC_{0-336h}$ , $C_{336h}$ , $C_{last}$ , $T_{last}$ , $\lambda_z$ , $T_{1/2}$

Individual subject concentration data and individual subject PK parameters for ADX will be listed and summarized using descriptive statistics by cohort. Summary statistics (n, mean, StD, coefficient of variation [%CV], median, min, max, Q1, and Q3) will be presented for both individual subject concentration data by time point and individual subject PK parameters by treatment. Moreover, the geometric mean, 95% CI, and the mean and StD of the natural log-transformed values will be presented for individual subject PK parameter data.

Individual concentration data listings and summaries will include all subjects with concentration data. The sample size for each time point will be based on the number of subjects with nonmissing concentration data at that time point. The number of subjects with concentration BLQ will be presented for each time point. For summary statistics, BLQ values will be treated as 0 at predose and one-half of the lower limit of quantitation (LLOQ) for postdose time points.

Individual PK parameter data listings and summaries will include all subjects for whom PK parameter(s) can be derived. The sample size for each PK parameter will be based on the number of subjects with nonmissing data for that PK parameter.

The following tables will be provided for each analyte by cohort:

- Individual subject concentration data and summary statistics
- Individual subject plasma PK parameters and summary statistics for Cohort 1

The following figures will be provided for each analyte for Cohort 1:

- Mean ( $\pm$  StD) concentration data versus time (on linear and semilogarithmic scales)
- Median (Q1, Q3) concentration data versus time (on linear and semilogarithmic scales)

Individual, mean, and median postdose concentration values that are  $\leq$  LLOQ will not be displayed in the figures and remaining points connected.

The following listings will be provided:

- PK sampling details by subject, including procedures, differences in scheduled and actual draw times, and sample age
- Individual data on determination of serum half-life and corresponding regression correlation coefficient

## **9. IMMUNOGENICITY ANALYSES**

### **9.1. ADA Sample Collection**

Serum samples will be collected to measure anti-ADX antibody (ADA) at protocol specified time points.

### **9.2. ADA Status**

A by-subject listing for ADA status at each time point and the titer for subjects with positive ADA status will be provided by subject ID number and time point in chronological order.

Immunogenicity data will be listed for all subjects in the Immunogenicity Analysis Set.

## 10. BIOMARKER ANALYSES

Binding of ADX to MMP9 will be evaluated in the periphery and additional biomarkers will be explored in blood and tumor tissue. A comprehensive analysis may be documented separately.

Biomarker Analysis Set will be used for biomarker analysis.

### 10.1. Statistical Analysis Methods

All summaries will be presented in tabular or graphical form. Descriptive statistics refers to number of subjects, mean, median, standard deviation (StD), 1st quartile (Q1), 3rd quartile (Q3), minimum, and maximum for continuous measurements and number and percentage of subjects in each level of a categorical measurement.

Tables will be provided for the following:

- Descriptive Statistics for free and total MMP9 by visit for Cohort 1
- Descriptive Statistics for the baseline level for biomarkers including EBV, MMR, and PD-L1 for Cohort 4

Figures will be provided for the following:

- Mean ( $\pm$  StD) Plot for free and total MMP9 over time for Cohort 1
- Median (Q1, Q3) Plot for free and total MMP9 over time for Cohort 1

Listings will be provided for the following:

- Free and total MMP9 for Cohort 1
- EBV, MMR, and PD-L1 for Cohort 4

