8.2.1.2. Pharmacokinetic/Pharmacodynamic Analysis Set

The PK/PD Analysis Set is defined as all subjects in the Safety Analysis Set who have the necessary baseline and on study measurements to provide interpretable results for specific parameters of interest.

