8.8. Biomarker Analysis

8.8.1. Pharmacodynamic Analysis

The pharmacodynamic biomarkers of interest are described in Section 3.11. The baseline level and change over time from baseline level will be evaluated. Descriptive statistics will be provided at each sampling time, by dose level.

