### **3.1.6. Biomarker Analysis Set**

The Biomarker Analysis Set will include subjects who took at least 1 dose of study drug and have at least 1 evaluable biomarker measurement available.

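### SAP 10.1 plans no change-from-baseline summary of MMP9 and no MMP9 output beyond Cohort 1, and does not record this as a departure from Protocol 8.8.1

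*SAP*

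**What the plan says.** **Protocol.** Section 8.8.1 states that "The baseline level and change over time from baseline level will be evaluated", and asks for descriptive statistics at each sampling time, grouped by dose level. The PK/PD Analysis Set in Section 8.2.1.2 is limited to treated subjects "who have the necessary baseline and on study measurements to provide interpretable results". Section 8.3 defines baseline as the most recent value before treatment and calls for changes from baseline where appropriate. Table 3-2 lists circulating MMP9 protein as a pharmacodynamic blood test in all four cohorts.

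**SAP.** Section 10 states the aim of evaluating andecaliximab binding to MMP9 in the periphery, and says a fuller analysis may be reported elsewhere. Section 10.1 then specifies:

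- a table: "Descriptive Statistics for free and total MMP9 by visit for Cohort 1";
- mean and median versions of a "Plot for free and total MMP9 over time for Cohort 1";
- a listing of free and total MMP9, again for Cohort 1.

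Section 10.1 defines descriptive statistics as counts, means, medians, standard deviations, quartiles and extremes. Change from baseline is not mentioned. Section 10 says the "Biomarker Analysis Set will be used for biomarker analysis", and Section 3.1.6 admits to that set any dosed subject with "at least 1 evaluable biomarker measurement available". Sections 6.2 and 7.7 record changes from the protocol for efficacy and safety. Section 10 records none.

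**The concern.** Whether an antibody engages its target is a within-subject question: does free MMP9 fall from that person's own starting level, and does it stay down? The protocol plans for this by naming change from baseline. The SAP's by-visit table of levels answers a different question, namely the average level among those sampled at a given visit.

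While the same subjects contribute at every visit, the two answers agree on the mean. They part once subjects leave, which happens here because treatment continues until progression. A difference between an early and a late visit mean then mixes drug effect with who remained. Even with complete data, the spread of individual changes cannot be read from the table.

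SAP 3.2 groups Cohort 1 at the single level of 800 mg Q2W. A by-dose-level presentation is therefore impossible from the planned output, and the only 1200 mg Q3W cohort (Cohort 3) is absent. With no declared departure, a reader of the study report would assume that Protocol 8.8.1 had been followed.

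**Working it through.** **1. Protocol and SAP side by side**

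| Element | Protocol | SAP |
|---|---|---|
| Quantity | Baseline level and change from it (8.8.1) | Level by visit; change not mentioned (10.1) |
| Grouping | By dose level (8.8.1) | Cohort 1 only, one dose level (10.1, 3.2) |
| Subjects | Baseline and on-study values (8.2.1.2) | One evaluable measurement (3.1.6) |
| Declared change | Not applicable | Yes for efficacy (6.2) and safety (7.7); none for biomarkers |

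That the table shows absolute levels is inferred from silence, but it is the ordinary reading: Section 10.1 describes its statistics and outputs in full and never mentions change.

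**2. What visit means cannot show, even with complete data.** Write SD for the standard deviation at each visit (taken as equal) and ρ for the correlation between a subject's baseline and later value. Then

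SD of change = SD × √(2(1 − ρ)).

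| Assumed ρ | SD of change |
|---|---|
| 0 | 1.41 SD |
| 0.5 | 1.00 SD |
| 0.7 | 0.77 SD |
| 0.9 | 0.45 SD |

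By-visit means and SDs do not identify ρ. The same table is compatible with a threefold range in the spread of individual changes (1.41/0.45 ≈ 3.1).

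**3. What drop-out does: a constructed example.** Assume six baselines of 50, 60, 70, 130, 140 and 150, with mean 600/6 = 100, and suppose every subject falls by exactly 20%.

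- If only the three lowest remain, the visit mean is (40 + 48 + 56)/3 = 48, an apparent fall of 52%.
- If only the three highest remain, it is (104 + 112 + 120)/3 = 112, an apparent rise of 12%.
- The within-subject change is −20% in both cases.

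**4. Random drop-out with no drug effect.** Neither document gives a variance, correlation or drop-out rate for MMP9, so the inputs are assumptions: lognormal levels, 6 subjects, 2 leaving at random, no change in anyone. The mean of the remaining 4 is compared with the mean of all 6 (200,000 replicates).

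| Assumed between-subject CV | Median absolute shift | 90th percentile |
|---|---|---|
| 40% | 7.6% | 18% |
| 60% | 11.0% | 26% |
| 80% | 14.1% | 32% |

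Hand check at a CV of 40%: the SD of the relative shift is about CV × √(1/4 − 1/6) = 0.40 × 0.289 = 11.5%. A normal approximation then gives a median of 0.674 × 11.5% = 7.8% and a 90th percentile of 1.645 × 11.5% = 19%, close to the simulated values.

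These figures illustrate later cycles only. They do not describe Cycle 1.

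**The case against.** The case on the other side has real force.

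- **Individual values will be visible.** SAP 10.1 lists free and total MMP9 for Cohort 1. With about six subjects, a reader can follow each one, and Section 10 leaves room for a separate fuller analysis. This stands as mitigation. But a listing is not a prespecified summary, and the separate analysis is optional with no stated content.
- **The scope is limited.** The SAP serves a synoptic report (SAP 1), and MMP9 is neither a primary nor a secondary endpoint. This stands and keeps the point modest. It does not explain why departures are recorded for efficacy and safety but not here.
- **The Cohort 1 restriction may be legitimate.** Protocol 3.11.1 allows tests to be dropped or added, and nothing shows that free and total MMP9 were assayed in Cohorts 2 to 4. This stands, so the request for those cohorts must be conditional. Dose is also confounded with combination partner: 1200 mg Q3W is given only with S-1 and oxaliplatin.
- **The broad analysis set has a purpose.** It also serves the EBV, MMR and PD-L1 baseline table for Cohort 4, where a post-dose value is irrelevant. This stands. The set need not change; only the change summary needs a paired condition.
- **Early visits are largely protected.** Cohort 1 is most densely sampled in Cycle 1, non-DLT withdrawals in the 28-day window are replaced (Protocol 6.11), and blood biomarkers are due both at screening and before the first dose (Protocol Appendix 2). This stands; the drop-out concern belongs to later cycles. The subject count at each visit will reveal the shrinkage but not correct for it.

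**Conclusion.** The point holds as a conflict between the two documents that the SAP does not declare. The protocol commits to change from baseline by dose level; the SAP prespecifies neither a change summary nor any MMP9 output outside Cohort 1. This follows from the text and needs no assumption beyond reading the by-visit table as absolute levels.

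The practical consequence depends on attrition and on variability the documents do not give. Under the assumptions above, losing 2 of 6 subjects moves a later visit mean by a median of 8% to 14%, and by 18% to 32% at the 90th percentile, with no one's level changing.

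Two stronger readings are tempting and should be resisted. A reader might infer that within-subject target engagement can never be estimated. The documents do not support that, since paired changes can be derived from the Cohort 1 listing and a separate analysis remains possible. A reader might also infer that precision is lost by comparing visits as if they were independent groups. With complete data the difference of visit means equals the mean paired change, and the SAP plans no unpaired standard error and no formal test (SAP 3.5).

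The SAP should be amended, but this is a descriptive pharmacodynamic output and the primary safety analysis is untouched.

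**What to change.** 1. In SAP 10.1, add absolute and percent change from baseline for free and total MMP9 by visit in Cohort 1. Take baseline as defined in Protocol 8.3. Restrict these outputs to subjects with a baseline and at least one post-dose value, and show the number of pairs at each visit.
2. Leave the Biomarker Analysis Set in SAP 3.1.6 as it is for other outputs, including the baseline-only table.
3. If free and total MMP9 were assayed in Cohorts 2 to 4, produce the same summary by cohort, with a note that dose is confounded with combination partner.
4. If they were not, or if the restriction is intended, add a statement to SAP 10 recording the limit to Cohort 1 as a change from Protocol 8.8.1.

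For Cohort 1 the cost is a paragraph of SAP text and one or two further tables built from values already due to be listed. No new samples or visits are needed. For the other cohorts the cost depends on whether assay results exist; recording the restriction costs one sentence.

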## **12. SOFTWARE**

SAS® Software Version 9.4. (SAS Institute Inc., Cary, NC, USA.) is to be used for all programming of tables, listings, and figures.

WinNonlin® (Pharsight Corporation, Mountain View, CA, USA.) is to be used for all PK analyses.

### 13. SAP REVISION

Revision Date (DD MMM YYYY)	Section	Summary of Revision	Reason for Revision

## 14. APPENDICES

- Appendix 1. Study Procedures Table – Cohort 1 (Andecaliximab Monotherapy)
- Appendix 2. Study Procedures Table – Cohort 2: Combination Therapy Andecaliximab and SP
- Appendix 3. Study Procedures Table – Cohort 3: Combination Therapy Andecaliximab and SOX
- Appendix 4. Study Procedures Table – Cohort 4: Combination Therapy Andecaliximab and Nivolumab

## SCHEDULE OF ASSESSMENTS

### Appendix 1. Study Procedures Table – Cohort 1 (Andecaliximab Monotherapy)

Cohort 1 (Andecaliximab Monotherapy)												
Study Phase	Screening	Each Cycle (28 Days)		Cycle 1				Every 8 Weeks k	EOT l	EOS	30-Day Safety Follow-Up m	5-Year LTFU r
Cycle Day	Screening	1	15	2	4	8	29/Cycle 2 Day 1 q	N/A	N/A	N/A	N/A	N/A
Window (Days)	-28		± 1		± 1	± 1		± 5	N/A	N/A	± 7	N/A
Study Assessments												
Informed Consent	X											
Medical History a	X											
Physical Exam b	X	X	X				X		X	X	X	
Vital Signs c	X	X	X	X	X	X	X		X	X	X	
12-Lead ECG	X	X					X			X		
ECOG Performance Status	X	X	X	X	X	X	X		X	X	X	
Prior/Concomitant Meds	X	X	X	X	X	X	X	X	X	X	X	
AEs d	X	X	X	X	X	X	X	X	X	X	X	
CT or MRI e	X							X		X		
Collect Archival Tumor Tissue (if available) f		X										

Cohort 1 (Andecaliximab Monotherapy)												
Study Phase	Screening	Each Cycle (28 Days)		Cycle 1				Every 8 Weeks k	EOT l	EOS	30-Day Safety Follow-Up m	5-Year LTFU r
Cycle Day	Screening	1	15	2	4	8	29/Cycle 2 Day 1 q	N/A	N/A	N/A	N/A	N/A
Window (Days)	-28		± 1		± 1	± 1		± 5	N/A	N/A	± 7	N/A
Sample Collection												
Chemistry	X	X h	X			X	X	X	X	X	X	
Hematology	X	X h	X			X	X	X	X	X	X	
Coagulation	X	X h	X				X	X	X	X		
Urinalysis	X	X h	X				X			X	X	
Pregnancy test s	X	X h								X	X	
Andecaliximab Concentration i		X	X	X	X	X	X		X	X	X	
Anti-Andecaliximab Antibodies j		X					X		X	X		
Blood Biomarkers n	X	X	X	X	X	X	X	X	X	X		
Tumor Tissue Biopsy o		X	X									
Normal Gastric Tissue Biopsy p		X										
Overall Survival and Other Antitumor Therapy												X (Every 3 months)
Study Drug Dosing												
Andecaliximab IV Dosing		X	X				X					

- EOS End of Study (visit); EOT End of treatment (visit); LTFU Long Term Follow Up; PE physical examination; PK: pharmacokinetics
- a. Medical history includes significant past medical events (eg, prior hospitalizations or surgeries), a review of the disease under study, prior anti cancer therapies, and any concurrent medical illnesses.
  - b. A complete PE will be performed at screening. A modified PE capturing changes from prior exams will be performed on Day 1 and 15 of each 28 day cycle, and at the EOT visit, at the EOS visit, and at the 30 day safety follow up visit. Weight (without shoes) should be measured at each PE and reported in kilograms. Height (without shoes) should be measured at screening only and reported in centimeters.
  - c. Vital signs include blood pressure, respiratory rate, pulse, and temperature. Measurements of blood pressure should be taken per institutional guidelines.
  - d. AEs will be assessed before and after andecaliximab dosing during applicable visits.
  - e. Tumor evaluation by CT or MRI will be performed during screening (scans taken as part of standard medical practice within 28 days of Day 1 are acceptable), every 8 weeks, and at the EOS visit (if not conducted within the previous 28 days). The same radiographic procedure used to define measurable lesions must be used throughout the study for each subject.
  - f. Archival tumor tissue FFPE blocks will be collected from all subjects. Efforts to acquire archival tissue block should begin on Cycle 1 Day 1.
  - g. For females of childbearing potential, a serum pregnancy test will be performed at screening and urine pregnancy tests will be performed on Cycle 1 Day 1 Pre Dose, at the EOS visit, and at the 30 day safety follow up visit.
  - h. Day 1 pre dose samples for the specified assessments may be drawn up to 2 days prior to the Day 1 visit.
  - i. Plasma samples for andecaliximab PK will be collected prior to andecaliximab dosing and 30 ( $\pm 15$ ) minutes after the end of infusion on Day 1 of Cycles 2, 3, 5, 7, and every 3 cycles thereafter, at the EOT visit (if not conducted in the last 2 weeks), and EOS visit. Additionally, PK plasma samples will be collected at the following time points in Cycle 1 only: 30 ( $\pm 15$ ) minutes after the end of infusion on Day 1; anytime on Days 2, 4, and 8; prior to dosing and 30 ( $\pm 15$ ) minutes after the end of infusion on Day 15
  - j. Blood samples for anti andecaliximab antibodies will be collected prior to dosing on Day 1 of Cycles 1, 2, 3, 5, 7, and every 3 cycles thereafter, at the EOT visit (if not conducted in the last 2 weeks), at the EOS visit, and at the 30 day safety follow up visit.
  - k. Every 8 Weeks ( $\pm 5$  days) assessments will be performed for subjects continuing treatment, or subjects who discontinue all treatment prior to disease progression but remain on study. If a subject *discontinues study drug (for example, as a result of an AE)*, every attempt should be made to keep the subject in the study to collect tumor assessments (CT/MRI), and blood samples for chemistry, hematology, coagulation, and blood biomarkers (if not collected in the last 2 weeks) every 8 weeks until disease progression.
  - l. EOT assessments will be requested by subjects who discontinue all treatment prior to disease progression. These assessments should be completed as soon as possible after the decision is made. Every attempt should be made to keep the subject in the study and continue to perform tumor evaluation by CT or MRI every 8 weeks until disease progression. Blood samples for hematology, coagulation, chemistry, blood biomarkers, andecaliximab concentration and anti andecaliximab antibodies should only be collected if not conducted in the last 2 weeks.
  - m. A safety follow up visit will be performed 30 days ( $\pm 7$  days) after the last dose of andecaliximab. The 30 day safety follow up visit may be substituted by a scheduled study visit if it occurs within the same window.
  - n. Blood samples for biomarkers will be collected Pre Dose on Day 1 of each cycle, Day 15 of Cycles 1 and 2, and every 8 weeks, at the EOT (if not conducted in the last 2 weeks) visit, and EOS visit. Additionally, blood samples for biomarkers will be collected on Days 2, 4, and 8 of Cycle 1.
  - o. Tumor tissue biopsy must be collected within 28 days prior to first dose and on Cycle 2 Day 15 (+ 5 days). Endoscopic samples (minimum 4, but 6-8 encouraged) to be processed as described in the laboratory manual.
  - p. Normal gastric tissue biopsy must be collected within 28 days prior to first dose (Day 1 of Cycle 1 Pre Dose). Endoscopic samples (minimum 4, but 6-8 encouraged) to be processed as described in the laboratory manual.
  - q. The Cycle 1 Day 29 visit, which overlaps with the Cycle 2 Day 1 visit, is the end of the DLT assessment window. In order for a subject to be evaluable for the DLT observation, the subject must have received the first dose of GS 5745, completed all safety procedures through Day 28, or have experienced a DLT prior to Day 28. Assessments should follow schedule for Day 1 of each 28 day cycle.
  - r. LTFU for OS begins after the EOS visit or the last visit on study if EOS does not occur. Subjects will be contacted via phone call every 3 months for determination of long term survival status and record of any other anti cancer therapy, cancer related surgery for up to 5 years after the EOS visit.

